6.1. Dose Modifications

Study Drug dose modifications will be performed as described in Table 6. All dose modifications must be recorded in the Dosage Administration electronic case report form (eCRF).

Table 6: Dose Titration

Titration*		Dose Regimen (imetelstat or equivalent volume of placebo)
0	Starting dose	7.5 mg/kg IV every 4 weeks
-1	Dose reduction #1	6.0 mg/kg IV every 4 weeks
-2	Dose reduction #2 (Minimum dose)	4.7 mg/kg IV every 4 weeks

Part 1 subjects whose dose was previously escalated (before Amendment 2) may continue at the 9.4 mg/kg dose.

6.1.1. Dose Modifications for Hematologic Toxicities

For any occurrence of Grade ≥ 3 thrombocytopenia or neutropenia, additional weekly blood counts should be performed until there is a return to baseline values. For treatment of hematologic toxicities, granulocyte-colony stimulating factors (G-CSF) are permitted for neutropenia as well as blood transfusions for anemia or thrombocytopenia.

The actions in Table 7 should be taken for Grade 3 hematologic toxicities present at the planned start of a dosing cycle. The actions in Table 8 should be taken for imetelstat-related Grade 4 hematologic toxicities at the planned start of a dosing cycle. It is recommended to contact the sponsor before discontinuing treatment due to Grade 3 or Grade 4 hematologic toxicity, particularly when the hematologic toxicity is without clinical consequences. Note that for Grade 3 or Grade 4 hematologic toxicities that are not considered related to imetelstat, the dose should still be held until recovery to ANC $1 \times 10^9/L$ and platelets $50 \times 10^9/L$.

Table 7: Dose Modifications for Grade 3 Hematologic Toxicities

Occurrence	Action
First	Hold study drug until recovery to ANC $1.0 \times 10^9/L$ and platelets $50 \times 10^9/L^*$; may restart at most recent dose level
Second	Hold study drug until recovery to ANC $1.0 \times 10^9/L$ and platelets $50 \times 10^9/L^*$; restart at 1 dose level lower
Third	Hold study drug until recovery to ANC $1.0 \times 10^9/L$ and platelets $50 \times 10^9/L^*$; restart at 1 dose level lower
Fourth	Discontinue study drug**

*For any other hematologic toxicities, the minimum counts for restarting should be at the Investigator's discretion

** Contact the sponsor to discuss the specific case before study drug is discontinued for hematologic toxicity

Table 8: Dose Modifications for Grade 4 Hematologic Toxicities

Occurrence	Action
First	Hold study drug until recovery to ANC $1.0 \times 10^9/L$ and platelets $50 \times 10^9/L^*$; restart at 1 dose level lower
Second	Hold study drug until recovery to ANC $1.0 \times 10^9/L$ and platelets $50 \times 10^9/L^*$; restart at 1 dose level lower
Third	Discontinue study drug**

*For any other hematologic toxicities, the minimum counts for restarting should be at the Investigator's discretion

** Contact the sponsor to discuss the specific case before study drug is discontinued for hematologic toxicity

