6. DOSAGE AND ADMINISTRATION

The term 'Study Drug' refers to treatment with either imetelstat or placebo.

Subjects may receive study drug until disease progression, unacceptable toxicity, or withdrawal of consent.

Supportive Care

All subjects will receive supportive care (including transfusions or myeloid growth factors) as needed per investigator discretion and according to local standard practices. Should an exceptional situation arise where it is deemed clinically necessary to give a transfusion for a Hb >11 g/dL, the reasons should be documented in the CRF.

Study Drug (Imetelstat or Placebo)

Imetelstat Sodium (GRN163L) for injection (imetelstat) is the investigational product in this study and will be provided by the sponsor.

Placebo will be supplied by the sponsor.

Study drug will be administered as a 2-hour IV infusion (\pm 10 minutes) at a constant rate using an infusion pump.

The baseline weight (ie, body weight determined at Screening) will be used to calculate the dose of study drug to the nearest 0.1 mg. The dose should be recalculated if there is a \geq 10% weight change from baseline. Note that the total dose may be recalculated more frequently (eg, at each study visit) depending on local practice. Study drug will be administered IV on a 28-day cycle.

The first dose of study drug should be administered within 72 hours of enrollment (Part 1) or randomization (Part 2) in IWRS.

All subjects in Parts 1 and 2 will receive a starting dose of 7.5 mg/kg of study drug given IV every 4 weeks. Subjects whose dose was previously escalated (before Amendment 2) may continue at the 9.4 mg/kg dose. Study drug dose delay or reduction for Grade 3 or Grade 4 toxicity will be instituted as needed, per the instructions provided in Table 7, Table 8, Table 9, Table 10, and Table 11. Note that these instructions are intended for Grade 3 or Grade 4 toxicities observed at the time of the planned dose on Day 1 of the next cycle. These instructions are not applicable when toxicities occur mid-cycle and subsequently resolve to Grade $<$ 3 by the time of the next planned dose.

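### Protocol Section 6.1.1 is inconsistent on whether drug-relatedness decides the dose action for a Grade 3 or Grade 4 cytopenia, so the same unrelated event can lead to different actions

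*Protocol*

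**What the plan says.** Five pieces of protocol text bear on the question.

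- **Table 7 sentence (Section 6.1.1).** "The actions in Table 7 should be taken for Grade 3 hematologic toxicities present at the planned start of a dosing cycle". Cause is not mentioned.
- **Table 8 sentence (Section 6.1.1).** "The actions in Table 8 should be taken for imetelstat-related Grade 4 hematologic toxicities at the planned start of a dosing cycle". Here relatedness is a condition.
- **Note (Section 6.1.1).** "Note that for Grade 3 or Grade 4 hematologic toxicities that are not considered related to imetelstat, the dose should still be held until recovery". Recovery is defined by neutrophil and platelet thresholds. The note does not give a restart dose, and does not say whether such an event counts as an occurrence in either table.
- **Table 8 title.** "Table 8: Dose Modifications for Grade 4 Hematologic Toxicities", without the condition used in the sentence that introduces it.
- **General rule (Section 6).** "Study drug dose delay or reduction for Grade 3 or Grade 4 toxicity will be instituted as needed, per the instructions provided in Table 7" and the tables that follow, again without a relatedness condition. Section 3.1 has a parallel sentence, also unqualified.

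Table 7 allows restart at the most recent dose after a first occurrence. For the second and third it says "restart at 1 dose level lower", and for the fourth "Discontinue study drug". Table 8 reduces at the first and second occurrence and discontinues at the third. Both tables carry the footnote "Contact the sponsor to discuss the specific case before study drug is discontinued for hematologic toxicity".

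Two further rules in Section 6 matter. The tables apply only to toxicity present on the planned Day 1 of a cycle. A hold that cannot end within 28 days because of toxicity leads to permanent discontinuation, with sponsor discussion for a responding subject. Neither rule refers to relatedness.

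**The concern.** An investigator who judges a Grade 3 neutropenia or thrombocytopenia unrelated to study drug finds two instructions. The Table 7 sentence brings the event under the reduction and discontinuation steps. The note suggests a hold and nothing more. For an unrelated Grade 4 event the lead-in sentence takes it out of Table 8 and leaves only the note, while the table's title and Section 6 put it back in. Two sites can handle the same event differently, and both can point to the protocol.

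Cytopenia is described as dose-limiting for imetelstat (Section 1.1.5.2.1) and is also listed as a disease-related anticipated event (Attachment 10). Attribution will therefore often be a real question. Section 6.1.3 shows that the protocol can settle it: Table 10 gives separate restart instructions for related and unrelated hepatic events. Section 6.1.1 uses relatedness without saying what follows from it.

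Anemia is a further gap. The footnote to Tables 7 and 8 refers to other hematologic toxicities, every subject enters transfusion dependent, and Attachment 10 lists anemia as disease-related. The note's recovery test nevertheless names only neutrophils and platelets.

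What is at stake is uniform exposure across sites and, through stopping, the primary endpoint. Under SAP Section 4.9.2.1 a qualifying 8-week transfusion-free period must start no later than 30 days after the last dose or at the End of Treatment visit, whichever is first.

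**Working it through.** The plan gives no figure to reproduce, so the main check is a comparison of the texts under each reading that a site could adopt.

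**Step 1. Three readings against the five texts**

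| Text | A: lead-in sentences taken literally | B: note governs unrelated events | C: tables apply whatever the cause |
|---|---|---|---|
| Table 7 sentence | agrees | conflicts (no exception for unrelated events) | agrees |
| Table 8 sentence | agrees | agrees | conflicts (the word imetelstat-related) |
| Note | replaces the table for Grade 4 but only adds to it for Grade 3 | agrees | redundant, since both tables already hold |
| Table 8 title | conflicts | conflicts | agrees |
| Section 6 rule | conflicts for Grade 4 | conflicts | agrees |
| *Unrelated Grade 3* | *Table 7 steps* | *hold only* | *Table 7 steps* |
| *Unrelated Grade 4* | *hold only* | *hold only* | *Table 8 steps* |

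Each reading leaves at least one text out of line, and the protocol does not say which governs. Every entry of hold only remains subject to the 28-day rule.

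**Step 2. Size for one subject with repeated unrelated Grade 3 events**

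Inputs are the dose levels in Table 6: 7.5, 6.0 and 4.7 mg/kg. Assume a start at 7.5, a restart at 7.5 after the first occurrence, and no reduction for another reason.

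- After the second occurrence under Table 7: 6.0/7.5 = 0.80, that is 20% lower.
- After the third: 4.7/7.5 = 0.627, that is 37% lower.
- At the fourth: discontinuation, after sponsor contact.
- Under the note alone: 7.5 mg/kg throughout.

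**Step 3. Can this reach the primary endpoint?**

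Entry requires ANC of at least 1.5 and platelets of at least 75 x 10^9/L (Section 4.1). For these two lineages a first Day 1 occurrence would therefore normally come no earlier than Cycle 2. The fourth would then come no earlier than Cycle 5 Day 1, which is 4 x 28 = 112 days (week 16) after Cycle 1 Day 1. The last dose would be at Cycle 4 Day 1, 3 x 28 = 84 days (week 12), or later if earlier holds shifted the cycles. The start window then closes at about 84 + 30 = 114 days, or 114/7 = 16.3 weeks, or at the End of Treatment visit if that is sooner.

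In the Part 1 target population the median onset of transfusion independence was 8.1 weeks, with a range of 0.1 to 33.1 (Section 1.1.5). At least half of those responses began well inside such a window. Late responses could be lost, but the documents do not allow a count.

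**Step 4. Frequency**

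Section 1.1.5.2.1 gives Part 1 rates of Grade 3 or higher neutropenia (34/57 = 59.6%), thrombocytopenia (31/57 = 54.4%) and anemia (10/57 = 17.5%). These count any cause and any day. The affected events are those judged unrelated, present on a planned Day 1 and, for reductions, recurrent. The documents give no number for them.

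**The case against.** The strongest reply is that the note settles the matter. It covers unrelated events of both grades in one sentence and says that the dose should *still* be held, which suggests that the tables were meant for related events only. On that view both grades get the same action and the gap is a missing qualifier in the Table 7 sentence. This is a fair reading. But it needs that qualifier to be supplied, and it leaves the Table 8 title and Section 6 unexplained.

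There are also safeguards. Discontinuation under Table 7 comes only at the fourth occurrence and after sponsor contact. Section 6.1.1 recommends such contact particularly when the cytopenia has no clinical consequences, and Section 10.2 asks investigators to consider continuing subjects who benefit. These stand. They attach to stopping, however, and not to the two reductions before it.

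Four stronger inferences are tempting, and the documents do not support them.

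- *That the protocol settles on a milder action for the more severe toxicity.* This is Reading A only. Readings B and C have no such inversion.
- *That an unrelated Grade 4 event can never lead to more than a hold.* The 28-day rule can end treatment whatever the cause.
- *That stable disease-related anemia on four Day 1 visits ends treatment.* The footnote leaves restart counts for other hematologic toxicities to the investigator. Section 12.1.1 describes adverse events as including what is new or aggravated from baseline, so unchanged baseline anemia is not plainly a toxicity. What remains is that its coverage is not stated.
- *That placebo subjects are handled differently because their cytopenias cannot be drug-related.* The note turns on what the investigator considers related. Investigators are to stay blinded at least until the primary analysis and may judge a placebo cytopenia possibly related. No bias between arms is shown.

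**Conclusion.** Wrong as written. The Table 7 sentence, the Table 8 sentence, the note, the Table 8 title and the Section 6 rule cannot all be followed for an event judged unrelated. This is a contradiction in an operative dosing rule, and goes beyond missing detail.

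For a subject with repeated unrelated Grade 3 events, the readings differ between an unchanged dose and reductions of 20% and then 37%, followed by discontinuation at the fourth occurrence after sponsor contact. This assumes the full starting dose and no other reason for reduction.

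How often this happens, and what it does to the 8-week transfusion-independence rate or to the treatment comparison, is not quantified and cannot be from these documents. A reader might take the Part 1 Grade 3 or higher rates as the size of the problem. They are not, because they are not limited to unrelated events or to Day 1. No view is taken here on which dosing rule is right.

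**What to change.** Reconcile the Table 7 sentence, the Table 8 sentence and title, the note, and the general rule in Section 6 (with its parallel in Section 3.1), so that the same event leads to one action at every site. The reconciled text should state:

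- whether an event judged unrelated counts as an occurrence toward reduction or discontinuation;
- whether disease-related anemia falls under Tables 7 and 8;
- that any difference in handling between Grade 3 and Grade 4 is intended, if one remains.

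The sponsor chooses the rule.

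The cost is wording in these sections and a memo to sites. No new data are needed, because investigators already record relatedness in the eCRF (Section 12.3.1). The correction keeps its value after the main study, since Section 6 carries the dose modification guidelines into the Extension Phase.

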6.1.2. Dose Modifications for Non-hematologic Toxicities, Excluding Hepatic Toxicities

The actions in Table 9 should be taken for Grade 3 or 4 non-hematologic/non-hepatic toxicities present at the planned start of a dosing cycle. For nausea and vomiting, only Grade 3 or 4 events which persist despite optimal antiemetic therapy should be considered for dose modification.

Table 9: Dose Modifications for Grade 3 and 4 Non-hematologic/Non-hepatic Toxicities

Occurrence	Action
First	Hold study drug until recovery to Grade ≤ 1 or baseline; restart at 1 dose level lower
Second	Hold study drug until recovery to Grade ≤ 1 or baseline; restart at 1 dose level lower
Third	Discontinue study drug

6.1.3. Dose Modifications for Liver Function Test Elevations and Hepatic Adverse Events

The actions in Table 10 should be taken for Grade 3 or 4 LFT elevations (AST, ALT and bilirubin), Grade 3 or 4 hepatic adverse events, and Grade ≥ 2 AST or ALT with Grade ≥ 2 bilirubin present at the planned start of a dosing cycle.

Table 10: Dose Modifications for Liver Function Test Elevations and Hepatic Adverse Events

Adverse Event	Action to be taken
Grade 3 or 4 AST, ALT, or bilirubin For ALT or AST $>8 \times ULN$ or baseline, contact sponsor and consider discontinuing drug altogether	
 • HOLD study drug and report as adverse event of interest (AEI) • Determine relatedness to study drug (i.e. extensive investigation^a to determine an alternative likely cause(s) for the event) 
 ○ If considered at least possibly related, after recovery to baseline, restart study drug at one dose level lower. ○ If not related, after recovery to baseline, restart study drug without dose reduction. • If the event recurs and is related, study drug should be discontinued

Adverse Event	Action to be taken
Grade 3 or 4 hepatic adverse event	
 • HOLD study drug and report as AEI • Determine relatedness to study drug (i.e. extensive investigation^a to determine an alternative likely cause(s) for the event) 
 ○ If considered at least possibly related, after recovery to baseline, restart study drug at one dose level lower. ○ If not related, after recovery to baseline, restart study drug without dose reduction. • If the event recurs and is related, study drug should be discontinued
Grade \geq 2 AST or ALT with concomitant Grade \geq 2 bilirubin* *Subjects with Grade 2 bilirubin at study entry should have worsening bilirubin with concomitant Grade 2 AST or ALT elevation	
 • HOLD study drug and report as AEI • Determine relatedness to study drug (i.e. extensive investigation^a to determine an alternative likely cause(s) for the event) 
 ○ If considered at least possibly related, discontinue study drug ○ If not related, after recovery to baseline, study drug can be restarted at same dose 
 ▪ If upon rechallenge the event recurs, study drug should be discontinued

^a Extensive investigation includes repeating liver enzyme and serum bilirubin tests with fractionation once or twice weekly until levels return to baseline. Obtain additional tests to evaluate liver function, as appropriate (i.e., INR, albumin). In addition, obtain a detailed history of symptoms, prior or concomitant disease, concomitant medications (including nonprescription herbal and dietary supplements), alcohol use, recreational drug use, special diets and environmental chemical agents. The following should be ruled out: acute viral hepatitis types A, B, C, D and E; autoimmune or alcoholic hepatitis; nonalcoholic steatohepatitis (NASH); hypoxic/ischemic hepatopathy; and biliary tract disease and may require gastroenterology and hepatology consultations. Consider hepatology (or gastroenterology) consultation. Document findings in the Imetelstat Questionnaire for Adverse Event of Interest eCRF.

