The study drug may be held for up to 28 days from the expected start date of the scheduled cycle; a hold $>$ 28 days must be reviewed and approved by the sponsor. The study drug should be discontinued permanently if it cannot be restarted within 28 days due to toxicity. If the subject is exhibiting an otherwise positive clinical response to treatment and the toxicity appears to be manageable, contact the sponsor to discuss the specific case before study drug is discontinued.

Treatment During the Extension Phase

Dose modification guidelines provided in the following sections will continue in the Extension Phase. Subjects may receive treatment in the Extension Phase until there is loss of benefit or unacceptable toxicity, as determined by the investigator according to local standard of care.

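### Protocol Table 10 orders both a reduced-dose restart and discontinuation for a first related combined liver elevation with a Grade 3 or 4 component, and no text says which row governs

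*Protocol*

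**What the plan says.** Protocol 6.1.3, Table 10 has three unnumbered rows, called rows 1 to 3 here. The lead-in names the three triggers side by side and limits the table to abnormalities present when a cycle is due to start. Section 6 adds that toxicities which arise mid-cycle and settle below Grade 3 by the next planned dose are outside the dose-modification instructions.

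- **Row 1**: any Grade 3 or 4 AST, ALT or bilirubin. Hold, report as an adverse event of interest, investigate. If related: "If considered at least possibly related, after recovery to baseline, restart study drug at one dose level lower". Above 8x ULN or baseline for ALT or AST, the site is asked to call the sponsor and think about stopping.
- **Row 2**: "Grade 3 or 4 hepatic adverse event". The restart wording is the same as in row 1.
- **Row 3**: AST or ALT at Grade 2 or above together with bilirubin at Grade 2 or above. Hold, report, investigate. If related: "If considered at least possibly related, discontinue study drug". A note narrows the row: "Subjects with Grade 2 bilirubin at study entry should have worsening bilirubin with concomitant Grade 2 AST or ALT elevation".

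The table stays in force later in the trial: "Dose modification guidelines provided in the following sections will continue in the Extension Phase" (Section 6).

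**The concern.** Row 1 is not confined to isolated elevations, and row 3 has no upper grade limit. The same event can therefore fall in both, and for a first related event the two orders cannot both be carried out. Following row 1 also reverses the safety logic: the milder combined event stops the drug, while the worse one may be re-dosed. The combined elevation is one that the protocol singles out as an adverse event of interest (Sections 9.8 and 12.3.3.1). Section 1.1.5.2.3 acknowledges that severe hepatobiliary events have occurred and that a link to imetelstat is not ruled out. What is at stake is consistent handling of subjects across sites, not an efficacy conclusion.

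**Working it through.** The plan states no figure on this point, so the check is logical, followed by what the documents say about frequency.

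**1. Cut-offs (Section 9.8).** AST/ALT: Grade 2 is above 3.0x ULN and Grade 3 is above 5.0x. Bilirubin: Grade 2 is above 2.0x ULN and Grade 3 is above 3.0x.

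**2. Overlap of rows 1 and 3.** Row 3 covers AST/ALT Grade {2, 3, 4} by bilirubin Grade {2, 3, 4}: 3 x 3 = 9 pairs. Row 1 needs at least one component at Grade 3 or 4.

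| AST/ALT | Bilirubin 2 | Bilirubin 3 | Bilirubin 4 |
|---|---|---|---|
| 2 | row 3 only | rows 1 and 3 | rows 1 and 3 |
| 3 | rows 1 and 3 | rows 1 and 3 | rows 1 and 3 |
| 4 | rows 1 and 3 | rows 1 and 3 | rows 1 and 3 |

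The overlap is 9 - 1 = 8 pairs. This counts table cells; it is not a frequency. Subjects who entered with Grade 2 bilirubin also need worsening bilirubin to meet row 3. A Grade 3 or 4 hepatic adverse event with laboratory values that meet row 3 overlaps rows 2 and 3 in the same way.

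**3. Actions in the overlap, first event.**

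| Causality | Row 1 | Row 3 | Compatible? |
|---|---|---|---|
| Not related | restart after recovery, dose unchanged | restart after recovery, dose unchanged | yes |
| At least possibly related | restart one level lower after recovery | discontinue | no |

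**4. Example** (related, subject on 7.5 mg/kg, bilirubin below Grade 2 at entry).

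- ALT 4x, bilirubin 2.5x ULN is Grade 2 with Grade 2. Of rows 1 and 3, only row 3 applies, so the drug stops.
- ALT 6x, bilirubin 2.5x ULN is Grade 3 with Grade 2. Row 1 permits restart at 6.0 mg/kg (Table 6), and row 3 requires stopping. ALT is below 8x ULN, so on that limb the sponsor-contact prompt need not fire.

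**5. Search for a ranking.** Section 6, Section 6.1.3 with its footnote, and Sections 9.8, 10.2, 11.12 and 12.3.3 contain none.

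**6. Frequency (Section 1.1.5.2.3), exact 95% intervals.**

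- Part 1, all enrolled: 0 of 57 consistent with Hy's Law. Upper limit 1 - 0.025^(1/57) = 6.3%.
- Part 1, target population: 3 of 38 with Grade 3 liver test elevations, 7.9% (1.7% to 21.4%). The hepatic committee judged none drug-related.
- Earlier study, MDS cohort: 0 of 9 with Grade 3 or 4 liver test abnormalities. Upper limit 1 - 0.025^(1/9) = 33.6%.

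None of these counts the overlap event itself, and the protocol does not define Hy's Law.

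**The case against.** The best reply is that the table resolves itself. Row 3 is the more specific rule, and both its components are open-ended upwards. If row 1 prevailed whenever a component reached Grade 3 or 4, row 3 would shrink to the single Grade 2 plus Grade 2 pair and its open-ended limits would do no work. Only precedence for row 3 gives every word effect and avoids the reversed logic.

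That is the better inference, but it remains an inference. Row 3's own note refers to a Grade 2 enzyme elevation ("Subjects with Grade 2 bilirubin at study entry should have worsening bilirubin with concomitant Grade 2 AST or ALT elevation"), so a site could reasonably treat row 3 as the Grade 2 plus Grade 2 row and row 1 as the rule for higher grades.

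The second reply is that practical exposure is small, and much of it stands. Both rows begin with the same hold, report and investigation. The event must reach the sponsor within 24 hours. Any restart needs recovery to baseline. Section 6 adds: "The study drug should be discontinued permanently if it cannot be restarted within 28 days due to toxicity", although it also asks sites to talk to the sponsor first about a responding subject whose toxicity looks manageable. Section 10.2 lets the investigator stop for safety, and the hepatic committee reviews cases at least quarterly. These controls lower the risk, but none says whether to restart.

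Two stronger readings are tempting and are not supported.

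- A reader might infer a second conflict over recurrence. Row 1 says "If the event recurs and is related, study drug should be discontinued"; row 3 says "If upon rechallenge the event recurs, study drug should be discontinued". Row 1's recurrence bullet is silent on an unrelated recurrence, so row 3 adds a stopping rule there and does not contradict an express instruction.
- A reader might apply the 6.3% limit to the 115 planned imetelstat subjects and treat the result as a ceiling. 115 x 0.0627 = 7.2 is only the expected count at that rate; a binomial count would exceed 7 with probability 0.43, and its 97.5th percentile is 13. Hy's Law is also only a proxy for the overlap event. The documents support no projected count.

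**Conclusion.** Table 10 is wrong as written on a narrow point of safety, of minor to moderate weight. The contradiction needs all of the following: a first event; causality at least possible; presence at the planned start of a cycle; AST/ALT and bilirubin both at Grade 2 or above with at least one at Grade 3 or 4; and worsening bilirubin if it was Grade 2 at entry. Within those limits it covers 8 of row 3's 9 grade pairs, and row 2 can collide with row 3 as well.

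How often this will arise is unknown and probably low, on the assumption that the sparse Part 1 data are a fair guide. No endpoint, error rate or power calculation is touched. It would be too strong to say that the plan intends re-dosing after severe combined injury: the wording of row 3 points the other way, and the defect is the missing order of precedence.

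**What to change.** Add one sentence to Table 10: *Row 3 governs over rows 1 and 2 whenever its combined criterion is met, whatever the highest single grade.* Number the rows so that the reference is clear.

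Section 17.1 requires a formal amendment with IEC/IRB approval, so bundle the change with the next amendment. It is still worth making because the table also governs dosing in the Extension Phase. The downside is possibly a few more permanent discontinuations, including some subjects who might have tolerated a lower dose.
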